8.3 ASSESSMENT OF SEVERITY

The following definitions of severity should be used in the evaluation of AEs:

- Mild: an AE that is easily tolerated and does not interfere with a subject's usual function or daily activities.
- Moderate: an AE that is sufficiently discomforting so as to interfere to some extent with a subject's usual function or daily activities.
- Severe: an AE that interferes significantly or prevents a subject's usual function or normal everyday activity.

The adjective selected should describe the maximum intensity of the adverse event.

8.4 ASSESSMENT OF RELATIONSHIP TO STUDY DRUG

The Investigator's assessment of causality must be provided for all adverse events (serious and non-serious) and recorded in the eCRF. An Investigator's causality assessment is the determination of whether there exists a reasonable possibility that the investigational product caused or contributed to an adverse event. If the Investigator does not know whether or not investigational product caused the event, then the event will be handled as "related to investigational product" for reporting purposes, as defined by the Sponsor. If the investigator's causality assessment is "unknown but not related to investigational product", this should be clearly documented on study records.

The following definitions of relationship to study drug should be used to characterize the suspected causality of each AE, based on the Principal Investigator's or licensed physician consideration of all available information:

- **Related:** A direct cause and effect relationship exists, or is likely to exist, between the AE and the study drug in the judgment of the investigator. (i.e., there is evidence or arguments to conclude that the study drug caused the adverse event)
- **Not Related:** The AE is not related to the study drug, if in the judgment of the investigator, there is not a reasonable possibility that the study drug may have caused the event (i.e., there is no evidence or arguments to suggest a causal relationship).

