9.3 SAFETY ANALYSIS

A treatment-emergent adverse event (TEAE) is defined as an AE that was not present at baseline, or an exacerbation of a pre-existing AE. For laboratory data, a treatment-emergent abnormal laboratory value (TEAV) represents an abnormal value that was normal at baseline.

Safety variables of analysis include the following:

- Proportions of patients with any TEAEs
- Proportions of patients with serious TEAEs
- Proportions of patients with severe TEAE
- Proportions of patients with TEAEs leading to study drug discontinuation
- Proportions of patients with TEAEs leading to study withdrawal
- Proportions of patients with drug-related TEAEs
- Proportions of patients with TEAVs
- Proportions of patients meeting DILI criteria
- Proportions of patients meeting ICH E14 criteria for threshold values or threshold changes
- Mean changes from baseline in vital signs
- Mean changes from baseline in clinical laboratory measures
- Mean change from baseline in measures from electrocardiography

Continuous data will be summarized by treatment group using descriptive statistics (number, mean, median, standard deviation, first and third quartiles, minimum, and maximum). Categorical data will be summarized by treatment group using frequency tables (frequencies and percentages).

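### Protocol section 8.4 sets two causality standards, so an event judged possible but not likely to be drug-related fits neither category and may be coded differently across sites

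*Protocol*

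**What the plan says.** Protocol section 8.4 requires a causality assessment for every adverse event, serious or not, and offers two categories. It contains four statements that bear on the choice.

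- **Lead-in.** The assessment is the "determination of whether there exists a reasonable possibility that the investigational product caused or contributed to an adverse event".
- **Default.** "If the Investigator does not know whether or not investigational product caused the event, then the event will be handled as" related, for reporting purposes as the sponsor defines them. The next sentence allows for an assessment of unknown cause but not drug-related, which must be documented.
- **Related bullet.** "A direct cause and effect relationship exists, or is likely to exist, between the AE and the study drug", explained as meaning that "there is evidence or arguments to conclude that the study drug caused the adverse event".
- **Not Related bullet.** In the investigator's judgment "there is not a reasonable possibility that the study drug may have caused the event", explained as meaning that "there is no evidence or arguments to suggest a causal relationship".

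The label is used in three places. Protocol section 9.3 lists "Proportions of patients with drug-related TEAEs" among its safety variables. SAP section 4.2.1 lists the corresponding proportion of subjects, and SAP section 5.3.1 plans TEAE summaries by relationship. Protocol section 8.7 makes the length of adverse event follow-up depend on the label. The SAP does not define relatedness and has no rule for unknown or missing causality.

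**The concern.** A two-category scale works only if the categories are complementary, so that every judgement falls in exactly one. Here one bullet is pitched at likelihood and the other at the absence of any reasonable possibility, and the explanatory phrases repeat the mismatch: evidence to conclude against evidence to suggest. The lead-in uses the lower standard and includes contribution to the event. The *Related* bullet raises the bar to a direct link and drops contribution.

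The judgement that falls between the bullets is a natural one here. Protocol section 1.1.3 reports concentration-related falls and confusion at 20 mg/day in the Phase 2 study, with no deleterious findings at 5 mg/day. SAP section 4.4 recognises that adverse events related to signs and symptoms of Alzheimer's disease may bear on both safety and efficacy. With no concurrent untreated group, an investigator may often think a drug effect possible without thinking it likely.

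At stake are the consistency of coding between sites, the meaning of the related-TEAE proportion in a study whose primary objective is long-term safety, and the follow-up of some unresolved events.

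**Working it through.** The documents state no figure on this point, so the check is one of logic. Sort the investigator's judgement into three states that cover every opinion:

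- **L**: a direct causal link exists or is likely.
- **P**: there is a reasonable possibility that the drug caused or contributed to the event, but it falls short of L.
- **N**: there is no reasonable possibility.

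Set each state against the three tests in section 8.4:

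| State | Lead-in test | Related bullet | Not Related bullet |
|---|---|---|---|
| L | met | met | not met |
| P | met | not met | not met |
| N | not met | not met | met |

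The bullets are mutually exclusive but not exhaustive, because P meets neither. The lead-in test does divide all three states cleanly: L and P on one side, N on the other. The section therefore contradicts itself over P.

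**Does the default resolve P?** Not clearly. It covers an investigator who does not know whether the drug caused the event. Judging an effect possible but not likely is an opinion and need not count as not knowing. The default is also limited to reporting purposes, and neither document says that it governs the analysis tables.

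**Effect on the tabulated proportion.** The unit is the patient. Let p(L) be the proportion of patients with at least one L event, and p(L or P) the proportion with at least one L or P event. Suppose L events are coded *Related* and N events *Not Related*. Among patients with a P event and no L event, let f be the fraction with at least one P event coded *Related*. Then:

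- reported related proportion = p(L) + f × [p(L or P) − p(L)]
- proportion under the lead-in standard = p(L or P)
- understatement = (1 − f) × [p(L or P) − p(L)]

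The understatement is zero at f = 1. At f = 0 it reaches its maximum, the share of patients with a P event and no L event. The documents give neither f nor that share, so no estimate is possible. Under these assumptions the lead-in proportion lies between the reported related proportion and the all-causality TEAE proportion, and both of those can be tabulated.

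**Effect on follow-up.** Under section 8.7, *Not Related* events are followed to resolution or for 60 days past the end of participation. *Related* events are followed to resolution or loss to follow-up. The label therefore matters only for events still unresolved at the 60-day point. The same section also lets the investigator, with the medical monitor, shorten follow-up with a written rationale.

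**The case against.** The strongest reply is that most of section 8.4 steers a possible event away from *Not Related*. The lead-in does, the *Not Related* bullet itself excludes any event with a reasonable possibility, and the default leans towards related. Only the *Related* bullet pulls the other way. Investigators may simply apply the lead-in, in which case nothing is understated. This stands as a limit on the consequence. It does not remove the contradiction, because the bullets are the definitions that investigators are told to use.

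The safeguards are also real. Protocol section 9.3 and SAP section 4.2.1 tabulate TEAEs regardless of causality, SAP section 5.3.1 lists causality event by event, SAP section 4.2 has medically qualified staff review the safety listings, and protocol section 9.6 gives all available safety data to the independent data monitoring committee. The SAP has no formal hypotheses and allocates no alpha.

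A reader might infer more than the text supports:

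- *That sites will code such events Not Related.* That bullet excludes them too, so the direction is possible but not certain.
- *That late SAEs will go unreported.* Protocol section 8.2 makes that report depend on a suspected causal relationship, and a possible effect can be suspected.
- *That a Not Related label simply cuts follow-up to 60 days.* Events that resolve earlier are unaffected.
- *That a primary endpoint is defined by relatedness.* Protocol section 2.2 names adverse events without a causality split, and the drug-related proportion is one of twelve variables listed in section 9.3.
- *That a given percentage of TEAEs would move.* The documents support no percentage, and a share of events is not a share of patients.

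**Conclusion.** The point holds as an inconsistency within protocol section 8.4. A possible but not likely drug effect passes the lead-in test and fits neither category, so two sites can each follow the section and code the same event differently. The descriptive proportion of patients with drug-related TEAEs may be understated, by anything from zero to the share of patients who have such an event and no likely-related one. That share cannot be obtained from the documents. The range assumes that likely events are coded *Related* and events with no reasonable possibility *Not Related*.

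Beyond the table, the label affects only the follow-up of events still unresolved 60 days after participation ends. Total TEAE capture, the all-causality tables and late SAE reporting are not affected. The correction is worth making because a tabulated safety variable currently rests on two conflicting definitions and the remedy is cheap.

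**What to change.** **Protocol and eCRF completion guidance.** Define *Related* by the lead-in's standard: a reasonable possibility that the study drug caused or contributed to the event. Delete the wording about a direct relationship that exists or is likely, together with its explanatory phrase. Word *Not Related* as the exact complement, including contribution.

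**SAP, sections 4.2.1 and 5.3.1.** State that unknown or missing causality is counted as related in the related-TEAE tables. Present the related proportion beside the all-causality proportion, with a note on which definition was in force when the events were assessed.

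**Cost.** The protocol change is a matter of wording and guidance, and the SAP change is one rule, one column and a footnote. The related rate may become less favourable, and some events may carry the longer follow-up duty. SAP section 1.5 says the study was terminated prematurely, so rewording the protocol may come too late to affect coding. The SAP steps remain available; they do not recode past events, but they show the reader the range within which the lead-in rate lies.

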8.5 SERIOUS ADVERSE EVENTS

A serious adverse event (SAE) is any AE that is fatal or life-threatening (see below), results in persistent or significant disability (see below) or incapacity, requires inpatient hospitalization or prolongation of an existing hospitalization, or is a congenital anomaly/birth defect.

Other important medical events that may not result in death, be life-threatening or require hospitalization should also be considered SAEs when, based upon appropriate medical judgment, they may jeopardize the study participant and may require medical or surgical intervention to prevent one of the outcomes listed above. Examples of such medical events include allergic bronchospasm requiring intensive treatment in an emergency room or at home or convulsions that do not result in inpatient hospitalization.

8.5.1 Life Threatening Adverse Event

A life-threatening AE is any AE that, in the view of the Principal Investigator, places the subject at immediate risk of death from the reaction as it occurred. A life-threatening AE would not be an AE that, had it occurred in a more serious form, might have caused death.

8.5.2 Disability

Disability is defined as a substantial disruption of a person's ability to conduct normal life functions.

8.5.3 Unexpected Adverse Event

An unexpected adverse drug experience is defined as “any adverse drug experience, the specificity or severity of which is not consistent with the current IB. For example, under this definition, hepatic necrosis would be unexpected (by virtue of greater severity) if the IB only referred to elevated hepatic enzymes or hepatitis. Similarly, cerebral thromboembolism and cerebral vasculitis would be unexpected (by virtue of greater specificity) if the IB only listed cerebral vascular accidents. Unexpected, as used in this definition, refers to an adverse drug experience that has not been previously observed (e.g., included in the IB), rather than from the perspective of such experience not being anticipated from the pharmacological properties of the pharmaceutical product.

Unexpected adverse events should be reported to the IRB/ Research Ethics Board (REB) as per IRB/REB reporting requirements.

8.6 DOCUMENTATION OF ADVERSE EVENTS

The condition of each study subject will be monitored throughout the study. Signs and symptoms of possible AEs may be observed by the staff, elicited by asking an open or indirect question (e.g., “How have you been feeling?”) or volunteered by the subject. All AEs, whether observed by the Investigator or clinical site staff, elicited from the subject, or volunteered by the subject, will be recorded. Data will include start and end dates, concomitant medications given for AE, Investigator-specified severity, relationship to study drug, and action taken. All AEs should be reported to the study Sponsor.

8.7 REPORTING REQUIREMENTS

The condition of each study subject will be monitored throughout the study. Signs and symptoms of possible AEs may be observed by the staff, elicited by asking an open or indirect question (e.g., “How have you been feeling?”) or volunteered by the subject. All AEs, whether observed by the Investigator or clinical site staff, elicited from the subject, or volunteered by the subject, will be recorded on the adverse event page(s) of the CRF. Data will include start and end dates, concomitant medications given for AE, Investigator-specified severity, relationship to study drug, and action taken.

Follow-up of any ongoing AE (including any clinically significant laboratory abnormality) should be conducted as follows:

- If the Investigator determines the AE is *not related* to the study product or study procedures, the AE will be followed until resolution, or 60 days from end of study participation.
- All AEs with a relationship of *related* will be followed until resolution, or until the subject is lost to follow-up.

At the discretion of the Investigator or designated licensed physician, in consultation with the Medical Monitor, the length of AE follow-up may be attenuated, with written rationale by the Investigator or designated licensed physician.

8.7.1 Serious Adverse Events Reporting Requirements

Knowledge of a SAE occurring or worsening in a subject at any time during the trial must be reported within 24 hours to the Safety Monitor. The site is responsible for reporting the event to the relevant IRB/REB in accordance with the IRB or REB's specific requirements for reporting SAEs. The Principal Investigator or designee should not wait to receive additional or follow-up information before an initial notification is made to the Sponsor.

Instructions related to SAE reporting, along with reporting forms and Sponsor contact information will be provided by the Sponsor to the Study Site and should be maintained in the Study Site File (SSF).

Reports relative to the subject's subsequent course must be submitted to the Safety Monitor until the event has subsided or, in the case of permanent impairment, until the condition stabilizes. These reports need not be submitted within 24 hours of first knowledge of each item of new information, unless the new information results in a change in diagnosis or represents a significant worsening of the subject's condition.

At any time following the study, the PI or designee should immediately notify the Sponsor and the IRB/REB if he/she learns of the occurrence of any malignancy involving the participant of a clinical trial or of any congenital anomaly in an offspring of a participant.

9.0 DATA ANALYSIS/STATISTICAL METHODS

The statistical considerations summarized in the following subsection outline the plan for data analysis of this study. A final and complete Statistical Analysis Plan (SAP) will be finalized prior to database lock for the study. The SAP will supersede the protocol. Any deviations from the planned analyses will be described in the final integrated study report.

This open-label, single-arm study includes subjects who completed TTP488-301, in which they were randomized to receive azeliragon (plus SoC) or placebo (plus SoC). An analysis plan for the meta-analysis combining data from TTP488-301 with this study will be done prior to database lock for this study. It is intended that the key analysis of results from this open-label study be described in the integrated analysis plan, and that the analysis of this study alone be described in this protocol.

SAS Version 9.4 or later will be used. Medical dictionary for Regulatory Activities (MedDRA) Version 18.0 or later will be used for coding adverse events. Medications will be coded using WHO Drug Dictionary (WHODD) Version March 2009 or later.

Continuous data will be summarized using descriptive statistics (number, mean, median, standard deviation, first and third quartiles, minimum, and maximum). Categorical data will be summarized for the enrolled population and also by treatment group according to the randomization of TTP488-301 using frequency tables (frequencies and percents).

Baseline will be the latest available data point prior to the first dose of study medication in this study (start of treatment for this protocol).

Outliers that are detected during the review of the data will be investigated. Methods for dealing with outliers will be defined in the SAP. In general, missing data will not be imputed, and outliers will not be excluded unless they are considered to be erroneous values.

9.1 POPULATIONS OF ANALYSIS

Populations of analysis are defined as follows:

- The full analysis set (FAS) includes all enrolled patients with on-treatment data. The FAS is used for all efficacy analyses.
- The per-protocol set (PPS) includes all FAS patients who are not excluded due to a significant protocol violation, where a significant protocol violation is one that has the potential to affect analysis conclusions. Final determinations of significant protocol violations will be made at the final blind data review meeting in accordance with guidance from ICH E9 (Statistical Principles).
- The safety set (SAF) includes all patients who received at least one dose of study medication. The SAF is used for all safety analyses.

To understand the impact of subjects who withdraw from the study prior to completion, the FAS will be partitioned into groups of subjects who complete the study (completers) and subjects who do not complete the study (dropouts).

9.2 DISPOSITION, DEMOGRAPHIC, AND BASELINE DATA

A tabulation of subject disposition will be presented, including the number enrolled for the single group of enrolled population, the number enrolled by treatment group according to the randomized treatment from Study TTP488-301, the number dosed in each population group, the number who withdrew prior to completing each part of the study, and reasons for withdrawal.

Demographic and baseline characteristics (disease history, medical history, and prior treatments) will be summarized for all randomized patients and for the FAS. No formal statistical comparisons will be performed.

9.3 SAFETY ANALYSIS

A treatment-emergent adverse event (TEAE) is defined as an AE that was not present at baseline, or an exacerbation of a pre-existing AE. For laboratory data, a treatment-emergent abnormal laboratory value (TEAV) represents an abnormal value that was normal at baseline.

Safety variables of analysis include the following:

- Proportions of patients with any TEAEs
- Proportions of patients with serious TEAEs
- Proportions of patients with severe TEAE
- Proportions of patients with TEAEs leading to study drug discontinuation
- Proportions of patients with TEAEs leading to study withdrawal
- Proportions of patients with drug-related TEAEs
- Proportions of patients with TEAVs
- Proportions of patients meeting DILI criteria
- Proportions of patients meeting ICH E14 criteria for threshold values or threshold changes
- Mean changes from baseline in vital signs
- Mean changes from baseline in clinical laboratory measures
- Mean change from baseline in measures from electrocardiography

Continuous data will be summarized by treatment group using descriptive statistics (number, mean, median, standard deviation, first and third quartiles, minimum, and maximum). Categorical data will be summarized by treatment group using frequency tables (frequencies and percentages).

9.4 EFFICACY ANALYSIS

Efficacy variables will include changes from baseline in scores from questionnaire data and cognition and performance assessments. Time to threshold changes will be defined in the SAP for the integrated analysis of the data from this study with the data from TTP488-301.

Continuous data will be summarized by treatment group using descriptive statistics (number, mean, median, standard deviation, first and third quartiles, minimum, and maximum). Categorical data will be summarized by treatment group using frequency tables (frequencies and percentages).

Baseline will be the latest available data point prior to start of treatment.

Outliers that are detected during the review of the data will be investigated. Methods for dealing with outliers will be defined in the SAP. In general, missing data will not be imputed, and outliers will not be excluded unless they are considered to be erroneous values. Sensitivity analyses and exploratory analyses may be done using imputation or excluding outliers to ensure robustness of study conclusions.

